## 5.1.3 Presentation of results

Unless mentioned otherwise tables will present TEAEs only.

The TEAE tables will be presented for the treatment and follow-up phase combined.

Tables to be produced for the topline results (see list of outputs in section 8.1) will be presented overall and by disease status at roll-over in 1905. These tables will show data for PV+PF participants as well as for PV participants.

_	SGS	Statistical Analysis Plan	
A	ARGX-113-1905	Final analysis	Final 1.0 of 26APR2024

An overview table will show the number and percentage of participants with at least one event, the incidence rate per 100 PYFU, the number of events and the event rate per 100 PYFU for the following:

- TEAEs
- Treatment related TEAEs
- Serious TEAEs
- Serious treatment related TEAEs
- Serious prednisone related TEAEs
- TEAEs of grade 3 or above
- Treatment-related TEAEs of grade 3 or above
- TEAEs related to prednisone
- TEAEs related to study procedures
- TEAEs for which the IMP was discontinued
- TEAEs for which the IMP was interrupted
- TEAEs of special interest
- Treatment related TEAEs of special interest
- TE IRR events
- Serious TE IRR events
- TE ISR events
- Fatal TEAEs

The overview table will be repeated specifically for ISR events, omitting the records related to TEAEs of special interest, prednisone-related TEAEs, IRR and ISR events.

A summary table by MedDRA system organ class and preferred term will show the number and percentage of participants with at least one event, the incidence rate per 100 PYFU, the number of events and the event rate per 100 PYFU. Each AE record in the clinical database is considered as a distinct adverse event and is counted as such.

The overview and summary tables mentioned above, will present:

- TEAEs
- post-TEAEs
- overall AEs (i.e., all AEs in the treatment + follow-up phase)

SGS	Statistical Analysis Plan	
ARGX-113-1905	Final analysis	Final 1.0 of 26APR2024

Separate tables will be prepared by MedDRA system organ class and preferred term showing the number and percentage of participants with at least one event, the incidence rate per 100 PYFU, the number of events and the event rate per 100 PYFU for the following:

- Most common TEAEs (>=5% in the Total group)
- Treatment related TEAEs
- Serious TEAEs
- Serious treatment related TEAEs
- Serious prednisone related TEAEs
- TEAEs of grade 3 or above
- Treatment-related TEAEs of grade 3 or above
- TEAEs related to prednisone
- TEAEs related to study procedures
- TEAEs for which the IMP was discontinued
- TEAEs of special interest
- Treatment related TEAEs of special interest
- TE IRR events
- Serious TE IRR events
- TE ISR events

All AEs, including pre-treatment events will be listed.

Separate listings will be prepared for serious AEs, AEs for which IMP was discontinued, fatal AEs and AESIs. A listing showing all coding information will be prepared as well.

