3. OBJECTIVES AND ENDPOINTS

Objectives	Endpoints				
Primary					
• To assess the safety of treatment, extended treatment, and retreatment with efgartigimod PH20 SC in participants with PV or PF	• Incidence and severity of treatment-emergent adverse events (TEAEs), adverse events of special interest (AESIs), and serious adverse events (SAEs) by system organ class (SOC) and preferred term (PT)				
	• Vital sign measurements, physical examinations, electrocardiograms (ECGs), and clinical laboratory safety evaluations				
Secondary					
• To evaluate the efficacy of efgartigimod PH20 SC treatment in PV and PF	Proportion of PV participants who achieve CRmin				
	• Proportion of PV and PF participants who achieve CRmin				
	• Time to DC				
	• Time to CR				
	• Time to CRmin				
	• Time to CRoff				
	• Time to flare				
	• Rate of treatment failure				
	• Rate of flare				
	• Cumulative prednisone dose over the trial				
	• Pemphigus Disease Area Index (PDAI) at each visit				
• To assess the health impact of glucocorticoid (GC) use in participants with PV or PF	• Composite Glucocorticoid Toxicity Index (C-GTI) comprising the Aggregate Improvement Score (AIS) and the Cumulative Worsening Score (CWS)				
• To evaluate the effects of efgartigimod PH20 SC on quality of life (QoL) in participants	• EuroQol 5-Dimension 5-Level (EQ-5D-5L) score				
with PV or PF	• Autoimmune Bullous Disease Quality of Life (ABQOL) score				
• To evaluate the pharmacokinetics (PK) of efgartigimod PH20 SC in participants with PV or PF	• Efgartigimod serum concentrations				
• To evaluate the PD of efgartigimod PH20 SC in participants with PV or PF	• Total IgG and subtype (IgG1, IgG2, IgG3, IgG4) serum levels				
	• Anti-Dsg-1 and -3 autoantibodies serum levels				

Objectives	Endpoints			
• To evaluate the immunogenicity of efgartigimod in participants with PV or PF	• Incidence and prevalence of antidrug antibodies (ADA) against efgartigimod (serum levels)			
• To explore feasibility of self-administration of efgartigimod PH20 SC	• Percentage of participants who performed self-administration			
	• Percentage of caregivers who administered the injection to the participant			
	• Number of visits needed for the participant or caregiver to be competent to start administering efgartigimod PH20 SC			
	• Frequency of self- or caregiver-supported administration at home			
Exploratory				

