At blinded rollover from ARGX-113-1904 into ARGX-113-1905 participants may be in different clinical stages. Participants may have achieved CRmin, participants may have achieved CR without meeting the minimal therapy criterion, participants may have achieved DC or EoC (the time at which no new lesions have developed for a minimum of 2 weeks and approximately 80% of lesions have healed) without having achieved CR, participants may have had treatment failure or a flare after having achieved CRmin.

ARGX-113-1905 evaluates the ability to (further) taper prednisone therapy and achieve CRoff, the ability to achieve CR and CRmin for participants who had not yet achieved CRmin, and the

ability to treat flare; and assesses patient outcome measures and the safety, PD, PK, and immunogenicity of efgartigimod PH20 SC over the duration of the trial. Duration of CR, time to CRoff and the effects of retreatment by the study drug will be specifically evaluated during the trial.

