#### **1.1 STUDY OBJECTIVES**

The primary objective of study 1905 is to assess the safety of treatment, extended treatment, and retreatment with efgartigimod co-formulated with rHuPH20 for subcutaneous (SC) administration (EFG PH20 SC) in participants with pemphigus vulgaris (PV) or pemphigus foliaceus (PF).

According to the protocol, the secondary objectives of this study are:

- To evaluate the efficacy of EFG PH20 SC treatment in PV and PF
- To assess the health impact of glucocorticoid (GC) use in participants with PV or PF
- To evaluate the effects of EFG PH20 SC on quality of life (QoL) in participants with PV or PF.
- To evaluate the PK of EFG PH20 SC in participants with PV or PF
- To evaluate the PD of EFG PH20 SC in participants with PV or PF
- To evaluate the immunogenicity of EFG in participants with PV or PF
- To explore feasibility of (self-)administration of EFG PH20 SC

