Follow-up		End of treatment phase + 1 minute		e of last contact, with 23:59 ed as time part.

a In case no 1905 ICF date is available, participant data will not be considered in the analysis

b Not applicable for participants who enter 1905 on CRmin. They will start immediately in Treatment period 2 of the Treatment phase in case of flare

A new treatment period is considered for participants with a flare after achieving CRmin (ie, while being off IMP treatment). A new treatment period is not considered after temporary IMP discontinuation for an adverse event. Repeat until the last on-treatment or off-treatment subperiod.

Participants who enter 1905 on CRmin, will not have a treatment period 1 in the treatment phase, but will start immediately with treatment period 2 at first IMP intake in 1905 (ie, after the first flare in 1905). Note: treatment period 2 is defined in 1905 as the treatment period starting after the first flare within 1905. Treatment given before a first flare in 1905 is considered belonging to treatment period 1.

Adverse events (AEs) and concomitant therapies will be allocated to phases and periods as described in sections 5.1.2 and 3.3.2 respectively. All other assessments will be allocated to phases (PDAI, PD, PK, albumin and LDL-C also to periods and subperiods) based on the assessment date(time).

In case of (partially) missing date(time) fields disabling allocation, information from the visit/timepoint label and protocol schedule of activities will be used to allocate to the correct phase, period and subperiod. If this is not possible (unscheduled visits or visits on a turning point between phases, periods or subperiods), assessments will be handled as follows:

- Treatment phase vs. roll-over phase: assessments will be allocated to the treatment phase unless the available parts of the assessments start or stop date/time provide evidence for allocating to the roll-over phase.
- Treatment phase vs. follow-up phase: assessments will be allocated to the treatment phase unless the available parts of the assessments start or stop date/time provide evidence for allocating to the follow-up phase.
- On-treatment vs. off-treatment subperiod within a treatment period: assessments will be allocated to the on-treatment subperiod unless the available parts of the assessments start or stop date/time provide evidence for allocating to the off-treatment subperiod.

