#### 5.1.2 Derivation rules

Treatment-emergent adverse events (TEAE) are defined as AEs starting on or after any administration of IMP in 1905 up through 60 days after the last administration of IMP prior to the AE.

Post-treatment AEs are defined as AEs that start after the 60 days after the last IMP administration prior to the AE. AEs that start during the roll-over phase are also considered as post-treatment AEs

Based on their start date/time, AEs will be allocated to the phase in which they started. Each AE will therefore be reported in only one phase. Phases are defined in section 2.2.1. In case the AE start date/time is incomplete or missing, and the AE could consequently be allocated to more than one phase, a worst-case allocation will be done in following order:

- Treatment phase vs. roll-over phase: the AE will be allocated to the treatment phase unless the available parts of the AE start and stop date/time provide evidence for allocating to the roll-over phase.
- Treatment phase vs. follow-up phase: the AE will be allocated to the treatment phase unless the available parts of the AE start and stop date/time provide evidence for allocating to the follow-up phase.

A death case is defined as an AE with outcome 'fatal'.

An AE for which the IMP was discontinued is defined as an AE with action taken 'drug withdrawn'.

Treatment relatedness will be dichotomized as follows in tables:

- Treatment related: related, probably related, possibly related or missing
- Not treatment related: not related, unlikely related

Page 49 of 84

SGS	Statistical Analysis Plan	
ARGX-113-1905	Final analysis	Final 1.0 of 26APR2024

Adverse events of special interest will be defined using MedDRA system organ class 'Infections and infestations'.

Injection-related reactions (IRRs) will be defined as all AEs with MedDRA preferred terms that are listed in either:

- Hypersensitivity standardized MedDRA query (SMQ) (broad selection)
- Anaphylactic reaction (SMQ) (broad selection)
- Extravasation events (injections, infusions and implants) (SMQ) (broad selection), excluding implants

AND occurring within 48 hours of an administration, or within 2 days in case no AE start time is available. In case of partially missing AE start date, the AE will be considered as an IRR, unless the available parts of the AE start date provide evidence it did not occur within 48 hours of an injection.

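### Retreatment safety is part of the primary objective, but the planned TEAE tables separate it from first and extended treatment only indirectly

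*SAP*

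**What the plan says.** SAP 1.1 states the primary objective as to "assess the safety of treatment, extended treatment, and retreatment" with efgartigimod PH20 SC, and protocol section 3 names the same three components. Protocol 4.2 adds: "Duration of CR, time to CRoff and the effects of retreatment by the study drug will be specifically evaluated during the trial".

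On allocation, the text after SAP Table 1 (section 2.2.1) says that AEs and concomitant therapies "will be allocated to phases and periods as described in sections 5.1.2 and 3.3.2 respectively". Section 5.1.2 then allocates each AE by start date to a phase and concludes: "Each AE will therefore be reported in only one phase". It gives no rule for treatment periods, and its partial-date rules also choose only between phases.

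On presentation, SAP 5.1.3 says "The TEAE tables will be presented for the treatment and follow-up phase combined". The topline AE tables are repeated by disease status at roll-over, in line with protocol 9.5.5. Under SAP 2.4.2 and 2.4.3, tables have separate columns for prior efgartigimod, prior placebo and total.

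**The concern.** AEs are the primary endpoint, and retreatment is one of the three exposures that the objective names. CRmin, CRoff, time to event, flare, prednisone dose, PDAI, PK and PD are all reported by treatment period. TEAEs are not.

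The documents give reasons to look at retreatment separately. Under protocol 6.1 (Table 3), a new cycle opens with an initial regimen (redacted) before weekly 1000 mg, while entrants in DC or CR start directly on weekly 1000 mg. Protocol 4.3 describes the subsequent weekly dose as the lower one, and 2.3.1 reports that injection-site abnormalities appeared to rise with SC dose in the phase 1 trial. At a flare, oral prednisone of 0.3 or 0.5 mg/kg is recommended, and protocol 8.3.7 names corticosteroids among the factors that can trigger or aggravate infections, which are the AESI. A difference confined to retreatment would be diluted wherever that time is pooled with period 1.

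**Working it through.** No hypothesis, power or sample-size figure bears on this point, so there is no figure of the plan's own to reproduce. The check has four steps.

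**1. Allocation and table list.** SAP 2.2.1 refers forward to 5.1.2 for period allocation, and 5.1.2 stops at phases. The rule in 2.2.1 for partial dates with multiple treatment periods belongs to the other assessments, not to AEs. Section 6.1 lists no related change. In SAP 8.1, none of tables 14.3.1.1.1 to 14.3.1.16.4 is by treatment period.

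**2. Can the AE subperiods in SAP Table 2 stand in?** They separate TEAEs from post-treatment AEs, and a new treatment-emergent subperiod opens only after a dosing gap of at least 61 days. Take a hypothetical participant with 20 weekly doses (days 1 to 134), a gap, then 12 weekly doses. That is two treatment periods.

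| Gap (days) | Retreatment starts | Treatment-emergent subperiods |
|---|---|---|
| 28 | day 162 | one: days 1–299 |
| 42 | day 176 | one: days 1–313 |
| 60 | day 194 | one: days 1–331 |
| 61 | day 195 | two: days 1–194 and 195–332 |
| 84 | day 218 | two: days 1–194 and 218–355 |

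At a 28-day gap, for example, the last dose is on day 162 + 11 × 7 = 239, and 239 + 60 = 299. Retreatment after a gap of 60 days or less merges with the earlier treatment, so these subperiods cannot replace periods.

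**3. What do the by-status AE tables isolate?** CRmin entrants have no period 1; their first 1905 dose opens period 2 after a flare (2.2.1). Those on CRmin who are dosed at roll-over are moved to the DC - no CR category (2.5, note 3).

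| Status at roll-over | Prior-efgartigimod column | Prior-placebo column |
|---|---|---|
| CRmin | retreatment only | first exposure, plus any later retreatment |
| Flare after CRmin | retreatment only | first exposure, plus any later retreatment |
| CR; DC - no CR; treatment failure | extended treatment, plus any later retreatment | first exposure, plus any later retreatment |

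Two of the ten status-by-arm columns therefore show retreatment alone. No table adds up all retreatment with its own participant-years of follow-up (PYFU).

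Period number is not a substitute label. SAP 2.2.1 places treatment given before a first flare within 1905 in period 1, so prior-efgartigimod participants who roll over in flare after CRmin are re-exposed in period 1. Placebo-arm CRmin entrants have their first exposure in period 2. The count of re-treatment periods in 3.4.2, which excludes period 1, has the same mislabelling.

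**4. Size of the dilution (assumed inputs).** Let f be the share of TEAE person-time that is retreatment and R the ratio of the retreatment rate to the first-period rate. Then pooled rate ÷ first-period rate = (1 − f) + f × R.

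| f | R = 1.5 | R = 2 |
|---|---|---|
| 0.1 | 1.05 | 1.10 |
| 0.2 | 1.10 | 1.20 |
| 0.3 | 1.15 | 1.30 |

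**The case against.** A reader might infer that the trial cannot show retreatment safety at all. The documents do not support that. Two prior-efgartigimod columns already show re-exposure, and the by-status split covers the AE overview (including injection-related reaction rows) and the SOC/PT tables for all TEAEs, serious and grade 3 or higher events, discontinuations, AESIs and injection site reactions. All AEs and all IMP administrations are listed, so rates by period can be derived without new data. The gap is in presentation.

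A reader might also infer that the CRmin stratum mixes re-exposed and first-exposed participants. Because tables are shown by 1904 treatment, that is true only of the Total column.

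Other points stand in part. Protocol 9.5.5 asks only for safety overall and by entry status, and the SAP delivers that; but this does not give the objective's third component a result of its own or settle the mismatch between 2.2.1 and 5.1.2. The protocol 4.2 sentence on retreatment sits beside efficacy measures and does not promise AEs by period. The contrast with other endpoints is not absolute: albumin and LDL-C have period-specific baselines and IMP administrations are summarised per period, while treatment failure and C-GTI are not reported by period. The analysis is purely descriptive, so no error rate is at stake.

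**Conclusion.** The point holds as a cheap improvement. The planned TEAE tables do not separate retreatment from first or extended treatment, except indirectly in the prior-efgartigimod columns of the CRmin and Flare after CRmin strata. For the other three entry categories, retreatment TEAEs are pooled with period 1 TEAEs, and no overall retreatment rate with its own PYFU is produced. The cross-reference from SAP 2.2.1 to 5.1.2 leads to a rule that is not there.

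The size cannot be fixed from the documents, which give neither the number retreated nor any 1905 event rate. Under the assumed range of 10% to 30% of person-time and a 1.5- to 2-fold rate, the pooled rate rises by only 5% to 30% over the first-period rate, so even a doubling in retreatment could pass unnoticed in a pooled column.

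**What to change.** In SAP 5.1.2, allocate each TEAE to the treatment period in which it starts, through 60 days after that period's last dose or until the first dose of the next period, whichever comes first. Add a matching partial-date rule and align 2.2.1 with it.

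Classify exposure by prior efgartigimod use, not period number:

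- First treatment: the first 1905 treatment period of prior-placebo participants, including period 2 for placebo-arm CRmin entrants.
- Extended treatment: period 1 of prior-efgartigimod participants who had not achieved CRmin.
- Retreatment: any treatment period after a flare following CRmin in a participant previously given efgartigimod, including period 1 of prior-efgartigimod Flare after CRmin entrants.

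State where prior-efgartigimod participants dosed at roll-over while on CRmin belong, since none of the three classes covers them.

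Repeat the AE overview and the SOC/PT tables for TEAEs, serious TEAEs, AESIs, injection site reactions and injection-related reactions by this class within each 1904 arm, with class-specific denominators and PYFU. SAP 2.4.1 already allows period-level denominators for event data.

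The cost is programming from dates already derived, plus extra tables; more if they are repeated for the regional subpopulations in SAP 2.4 and for PV participants. Retreatment columns may be small. With an assumed 20 retreated participants and no events of a given type, the one-sided 95% upper bound is still 1 − 0.05^(1/20) = 13.9%, so the tables should be read as descriptive.

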#### 5.2 CLINICAL LABORATORY EVALUATION

#### 5.2.1 Available data

Per protocol, the following safety laboratory parameters are expected:

- Biochemistry: sodium, potassium, total calcium, HbA1c, creatinine, creatinine clearance (adjusted for BSA), blood urea nitrogen (BUN), alanine aminotransferase (ALT), aspartate aminotransferase (AST), total bilirubin, gamma-glutamyl transferase (GGT), low-density lipoproteincholesterol (LDL-C), C-reactive protein (CRP), alkaline phosphatase (AP), lactate dehydrogenase (LDH), uric acid, total protein, and albumin
- Hematology: hemoglobin, hematocrit, mean corpuscular volume (MCV), red blood cell (RBC) count, platelet count, white blood cell (WBC) count with differential
- Urinalysis: color, clarity/appearance, specific gravity, pH, protein, glucose, ketones, blood, bilirubin, urobilinogen, nitrite, leukocyte esterase, and microscopic examination of RBCs, WBCs, casts, crystals, and bacteria

Normal ranges are available as provided by the laboratory.

SGS	Statistical Analysis Plan	
ARGX-113-1905	Final analysis	Final 1.0 of 26APR2024

## 5.2.2 Derivation rules

Toxicity grades will be computed according to the NCI CTCAE toxicity grading list (version 5.0). The implementation of these toxicity grades for analysis is presented in appendix 9.2. Only the parameters described in appendix 9.2 will be computed, according to the declared limits for each grade.

The following abnormality categories will be defined for parameters with no toxicity grade available:

- Low: value < lower limit of normal range
- Normal: lower limit of normal range ≤ value ≤ upper limit of normal range
- High: value > upper limit of normal range

Notes:

- Classification will be done by using non-imputed values and limits as reported in standardized units in the clinical database: a value <X where X equals the lower limit of normal range will be classified as low. A value X with normal range <X will be classified as high.
- For the worst-case analysis visits as defined in section 2.2.5, an additional category low + high is defined in case there are both low and high post-baseline values.

The estimated glomerular filtration rate (eGFR) will be derived by the Chronic Kidney Disease Epidemiology Collaboration (CKD-EPI) formula, if not already provided as such by the lab:

eGFR (mL/min/1.73m^2) = 141 \* minimum(creatinine (mg/dL)/ K; 1) $\alpha$  \* maximum(creatinine (mg/dL)/ K; 1) -1.209 \* 0.993age (years) \* [1.018 if female] \* [1.159 if race = black]

where K = 0.7 if female and K = 0.9 if male;

 $\alpha$  = -0.329 if female and  $\alpha$  = -0.411 if male

Note: in case results in mg/dL are not available, results in  $\mu$ mol/L will be used after conversion in mg/dL: 1 mg/dL = 88.4  $\mu$ mol/L

#### 5.2.3 Presentation of results

The statistical analysis will present results in standardized units, except for eGFR, which will be reported in mL/min/ $1.73m^2$ .

Continuous laboratory parameters will be summarized by means of descriptive statistics of the actual values and changes from baseline at each analysis visit. For albumin and LDL-C, also percent changes from baseline will be shown. Categorical parameters will be listed only.

Laboratory abnormalities will be presented as cross-tabulations of the abnormality at each post-baseline analysis visit and at the worst-case analysis visit versus the baseline abnormality. This table will also show numbers of participants with treatment-emergent abnormalities (see Definition of terms). The denominator for the percentage is the total number of participants per treatment and per analysis visit in

SGS	Statistical Analysis Plan	
ARGX-113-1905	Final analysis	Final 1.0 of 26APR2024

the Safety analysis set. Abnormalities will not be tabulated for those parameters for which toxicity grades are defined.

Laboratory toxicity grades will be presented as cross-tabulations of the toxicity at each post-baseline analysis visit and at the worst-case analysis visit versus the baseline toxicity. This table will also show numbers and cumulative numbers over decreasing toxicity grading of participants with treatment-emergent toxicities. The denominator for the percentage is the total number of participants per treatment and per analysis visit in the Safety analysis set. Parameters having toxicity grades defined in both directions (hypo and hyper) will be shown by direction.

Tables to be produced for the topline results (see list of outputs in section 8.1) will show data for PV+PF participants as well as for PV participants.

All laboratory data will be listed, but only for participants with any post-baseline abnormality/toxicity or clinically significant value.

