# **DEFINITION OF TERMS**

Case report form (CRF)	A printed, optical, or electronic document designed to record protocol required information to be reported to the sponsor for each study participant.
Complete clinical remission (CR)	The absence of new lesions and complete healing of established lesions (except for post-inflammatory hyperpigmentation or erythema from resolving lesions).
Complete remission on minimal therapy (CRmin)	The absence of new and established lesions completely healed while the participant is receiving prednisone therapy at $\leq 10$ mg/day for at least 2 months (8 weeks).
Complete remission off therapy (CRoff)	The absence of new and established lesions completely healed while the participant is receiving no prednisone therapy for at least 2 months (8 weeks).
Disease control (DC)	The absence of new lesions and the start of healing of established lesions.
Disease progression	Increase of $\geq$ 5 points in the PDAI activity score, observed at any post-baseline visit before DC.
Display	Analysis table, listing or figure
End of consolidation (EoC)	The time at which no new lesions have developed for a minimum of 2 weeks and approximately 80% of lesions have healed.
Flare	The appearance of 3 or more new lesions in a 4-week period that do not heal spontaneously within 1 week or the extension of established lesions, in a participant who had achieved DC.
Phase	Interval of time in the planned conduct of a study that is associated with a specific purpose: for example, screening, treatment, follow-up.

SGS	Statistical Analysis Plan		
ARGX-113-1905	Final analysis	Final 1.0 of 26APR2024	
Significant digit	All digits of a number used to express it to the required degree of accuracy, starting from the first non-zero digit.		
Standardized unit	unit populating –STRESU in the clinical database		
Study drug or investigational medicinal product (IMP)	Pharmaceutical form of an active ingredient or placebo, being tested or used as a reference in a clinical study.		
Treatment-emergent abnormality / toxicity	Any post-baseline abnormality/toxicity that was not present at baseline (e.g. hemoglobin normal or missing at baseline and grade 1 post-baseline; glucose low at baseline and high post-baseline; QTcF ]450; 480] ms at baseline and >500 ms post-baseline)		

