	mg/dL	<lln-1.2< td=""><1.2-0.9	<0.9-0.7	<0.7	</lln-1.2<>	<1.2-0.9	<0.9-0.7	<0.7
Magnesium high [1]	mmol/L	>ULN-1.23	-	>1.23-3.30	>3.30
	mg/dL	>ULN-3.0	-	>3.0-8.0	>8.0
Potassium low [1]	mmol/L	-	<lln-3.0< td=""><3.0-2.5	<2.5	</lln-3.0<>	<3.0-2.5	<2.5
	mEq/L	-	<lln-3.0< td=""><3.0-2.5	<2.5	</lln-3.0<>	<3.0-2.5	<2.5
Potassium high 	mmol/L	>ULN-5.5	>5.5-6.0	>6.0-7.0	>7.0
	mEq/L	>ULN-5.5	>5.5-6.0	>6.0-7.0	>7.0
Sodium low 	mmol/L	<lln-130< td="">-	<130-120	<120	</lln-130<>	-	<130-120	<120
	mEq/L	<lln-130< td="">-	<130-120	<120	</lln-130<>	-	<130-120	<120
Sodium high 	mmol/L	>ULN-150	>150-155	>155-160	>160
	mEq/L	>ULN-150	>150-155	>155-160	>160
Triglycerides	mmol/L	1.71-3.42	>3.42-5.70	>5.70-11.4	>11.4
	mg/dL	150-300	>300-500	>500-1000	>1000
Partial thromboplastin time (activated or not specified		>1.0-1.5 *ULN	>1.5-2.5 *ULN	>2.5 *ULN	-

Page 74 of 84

CONFIDENTIAL AND PROPRIETARY

SGS													
ARGX-113-1905		Final analysis											
CD4 count 	giga/L	<lln-0.50< th=""><0.50-0.20	<0.20-0.05	<0.05	</lln-0.50<>	<0.50-0.20	<0.20-0.05	<0.05								
	counts/mm3	<lln-500< td=""><500-200	<200-50	<50	</lln-500<>	<500-200	<200-50	<50								
Fibrinogen		<1.00-0.75 *LLN	<0.75-0.50 *LLN	<0.50-0.25 *LLN	<0.25 *LLN								
International normalized ratio		>1.2-1.5 *ULN	>1.5-2.5 *ULN	>2.5 *ULN	-								
Lymphocytes (absolute count) low [1]	giga/L	<lln-0.80< td=""><0.80-0.50	<0.50-0.20	<0.20	</lln-0.80<>	<0.80-0.50	<0.50-0.20	<0.20								
	counts/mm 	<lln-800< td=""><800-500	<500-200	<200	</lln-800<>	<800-500	<500-200	<200								
Lymphocytes (absolute count) high	giga/L	-	>4-20	>20	-								
	counts/mm 	-	>4000-20000	>20000	-								
Neutrophils (absolute count) 	giga/L	<lln-1.5< td=""><1.5-1.0	<1.0-0.5	<0.5	</lln-1.5<>	<1.5-1.0	<1.0-0.5	<0.5								
	counts/mm 	<lln-1500< td=""><1500-1000	<1000-500	<500	</lln-1500<>	<1500-1000	<1000-500	<500								
Platelets 	giga/L	<lln-75< td=""><75-50	<50-25	<25	</lln-75<>	<75-50	<50-25	<25								

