	counts/mm 	<lln-75000< td=""><75000-50000	<50000-25000	<25000	</lln-75000<>	<75000-50000	<50000-25000	<25000								
White blood cells 	giga/L	<lln-3< td=""><3-2	<2-1	<1	</lln-3<>	<3-2	<2-1	<1								
	counts/mm 	<lln-3000< td=""><3000-2000	<2000-1000	<1000	</lln-3000<>	<3000-2000	<2000-1000	<1000								

 In case ULN/LLN is higher/lower than the upper/lower limit of grade 1 (or even higher grades), ULN/LLN will be ignored and only the fixed values of CTCAE will be considered. In case ULN/LLN is missing, a grade will only be derived if the value leaves no doubt on which grade is to be assigned.

Document template OTH.STAT.010 v3
-----------------------------------

Page 75 of 84

CONFIDENTIAL AND PROPRIETARY

SGS	Statistical Analysis Plan	
ARGX-113-1905	Final analysis	Final 1.0 of 26APR2024

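### White-cell, neutrophil and platelet counts above normal are counted in no laboratory shift, treatment-emergent or worst-case table, because graded parameters are excluded whole although these three are graded only downwards

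*SAP*

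**What the plan says.** Two rules in the SAP's laboratory section work together. Section 5.2.2 introduces the low/normal/high scheme with the words "The following abnormality categories will be defined for parameters with no toxicity grade available". Section 5.2.3 then says that "Abnormalities will not be tabulated for those parameters for which toxicity grades are defined". Both are worded by parameter, not by direction.

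Grades come only from Appendix 9.2: "Only the parameters described in appendix 9.2 will be computed, according to the declared limits for each grade". There, the row "White blood cells" and the rows for absolute neutrophils and platelets each carry limits below normal only. Lymphocytes differ: they have a low row and a second row, "Lymphocytes (absolute count) high". For the toxicity table, 5.2.3 adds that "Parameters having toxicity grades defined in both directions (hypo and hyper) will be shown by direction".

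The laboratory listing (16.2.8.1) is restricted to participants with at least one post-baseline abnormality or toxicity, or a clinically significant value.

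**The concern.** Clinical laboratory evaluation is part of the primary safety endpoint (protocol Sections 3 and 9.1.2), and the shift and worst-case tables are where a reader looks for how many participants left the normal range. For three blood counts those tables can answer in one direction only. A reader who finds no high white-cell or neutrophil category could take that as absence of such values, when the rule prevents them from being counted. The trial names infection as its event of special interest (protocol 8.4.8, SAP 5.1.2) and gives prednisone alongside the study drug, so high counts are values a safety reviewer would want to see tabulated.

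It looks like an oversight. Lymphocytes, potassium, sodium, calcium and magnesium are graded both ways in Appendix 9.2, and SAP 5.3.2 and 5.4.2 classify vital signs, ECG heart rate and PR in both directions.

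**Working it through.** No arithmetic is involved. The check follows one post-baseline value above the upper limit of normal (ULN) through the rules.

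**Inputs.** Appendix 9.2 limits in giga/L, where LLN is the lower limit of normal, together with the rules in SAP 5.2.2, 5.2.3, 2.2.4, 2.2.5 and 2.4.1.

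| Parameter | Graded low | Graded high | Value above ULN gets a grade? | Low/normal/high derived? |
|---|---|---|---|---|
| White blood cells | <LLN-3, <3-2, <2-1, <1 | none | no | no, parameter is graded |
| Neutrophils (absolute) | <LLN-1.5, <1.5-1.0, <1.0-0.5, <0.5 | none | no | no, parameter is graded |
| Platelets | <LLN-75, <75-50, <50-25, <25 | none | no | no, parameter is graded |
| Lymphocytes (absolute) | <LLN-0.80 down to <0.20 | >4-20 (grade 2), >20 (grade 3) | yes, if above 4 | no, and high values are graded |

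1. **Table 14.3.2.4 (abnormalities).** The first three parameters are excluded because they have a grade. High values are absent.
2. **Table 14.3.2.5 (toxicity grades).** A value above ULN meets none of the low limits, so it counts as no toxicity. The by-direction display helps only parameters graded both ways.
3. **Treatment-emergent counts.** These are part of the same two tables, so high values are not counted there either.
4. **Worst-case visit.** SAP 2.2.5 builds it from all post-baseline values in the treatment and follow-up phases, including unscheduled ones, for parameters with abnormalities and/or grades. For laboratory data, 5.2.2 and 5.2.3 make the two mutually exclusive, so no high worst case arises for these counts.
5. **By-visit statistics (Table 14.3.2.1).** High values do enter. SAP 2.4.1 includes the quartiles and the maximum, but gives no count of participants above ULN. SAP 2.2.4 keeps only the value nearest the target day in each window, so a count from an unscheduled visit may not be used.
6. **Listing.** A high count alone is neither an abnormality nor a toxicity under these rules. It triggers the listing only if judged clinically significant.

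Of these four graded blood counts, three have no count of high values in the shift, treatment-emergent or worst-case tables. No other section of the SAP restores one.

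**The case against.** The strongest reply is that little is lost, and much of it stands.

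- The listing is triggered per participant, not per parameter. One out-of-range ungraded result, such as CRP, LDH or uric acid, brings in all of that participant's laboratory data, high counts included.
- Protocol 8.3.6 makes a clinically significant laboratory abnormality an adverse event, so it reaches the AE tables. The same section allows a value consistent with a current diagnosis to be documented without a separate AE.
- Infection is measured directly. The whole infections system organ class is the special-interest category, with its own overview, preferred-term and disease-status tables. High CRP is tabulated because it is ungraded, high temperature is tabulated, and high lymphocytes are graded.
- If the differential is also reported as percentages, those ungraded fractions could be tabulated. The documents do not say.
- The study is descriptive and tests no hypothesis (protocol 9.2).

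A reader might therefore infer too much from the rule trace, in two ways. The first is that the report would show no high counts at all. The documents do not support that: the by-visit maximum, the listing and the AE tables can all carry them. The second is a number of hidden participants, reached by applying an assumed rate of high neutrophils on prednisone to the 213 in SAP 1.3. The documents give no such rate, and 213 is the maximum who could roll over. The laboratory tables use the Safety analysis set, which leaves out anyone not dosed in this study.

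None of this answers the core point: no table says how many participants rose above normal on these counts, or shifted there from baseline.

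**Conclusion.** The concern holds as a display gap in a primary safety outcome. For white blood cells, neutrophils and platelets, the number of participants shown above normal in Tables 14.3.2.4 and 14.3.2.5 is zero by rule. That rests only on reading 5.2.2, 5.2.3 and Appendix 9.2 as written. How many participants this affects cannot be stated from the documents. The infection assessment does not depend on these counts, so the consequence is an incomplete laboratory display, not a missed safety endpoint. It is still worth correcting before the tables are programmed.

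A minor related point concerns hemoglobin. The SAP's Definition of terms illustrates a treatment-emergent toxicity with "hemoglobin normal or missing at baseline and grade 1 post-baseline", but Appendix 9.2 as available shows no hemoglobin row. A reader might infer that the SAP promises a hemoglobin grade and fails to deliver it. That goes too far: the wording is an example in what looks like a generic definition, and the table is damaged in the text version, so a row may have been lost. If there is truly no row, hemoglobin falls under low/normal/high and is tabulated in both directions, without severity.

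**What to change.** Reword SAP 5.2.2 and 5.2.3 so that the exclusion applies by direction. Where Appendix 9.2 grades a parameter in one direction only, classify the ungraded direction against the laboratory normal range and include it in the shift, treatment-emergent and worst-case tables. Let such a value count as an abnormality for the listing trigger. This should cover at least white blood cells, neutrophils and platelets. Albumin is also graded low only, and the sponsor can decide whether its high direction is worth showing.

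Separately, reconcile the hemoglobin example in the Definition of terms with Appendix 9.2, by confirming the row or changing the example.

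The cost is a change of SAP wording, a small change to the derivation and a few more table pages. SAP 5.2.1 says normal ranges are already supplied by the laboratory, so no new data are needed.
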